Regardless of how long participants have been on Oxbryta® (Voxelotor) when they enroll in the study, participants will be followed for up to 5 years after their first dose of Oxbryta® (Voxelotor) treatment, or until they withdraw their consent to participate, or are discontinued from the study. Treatment, including interruptions and restarting treatment, will continue at the discretion of the treating physician, and there are no pre-defined treatment requirements. Participants may receive any additional medications prescribed by their treating physician or have any medical interventions that are deemed appropriate by the treating physician or study doctor. The participant or treating physician may discontinue Oxbryta® (Voxelotor) at any time. Participants who discontinue treatment with Oxbryta® (Voxelotor) earlier than 5 years will continue to be followed on study to collect clinical and health-related quality of life (HRQoL) outcomes for up to 5 years after their first dose of Oxbryta® (Voxelotor) treatment.

Participant safety and tolerability will be assessed throughout the study data collection period by the study doctor and reported to the Sponsor.

The overall study design is illustrated in [Figure 1](#).

Figure 1: Study Schema

SOC, standard of care.

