| Urine Creatinine | Effectiveness endpoint measures – Renal function | Case report form | Captured from laboratory assessment- Renal function form |
| Albumin Creatinine Ratio (ACR) | Effectiveness endpoint measures – Renal function | Case report form | Captured from laboratory assessment- Renal function form |
| Hemoglobinuria | Effectiveness endpoint measures – Renal function | Case report form | Captured from laboratory assessment- Renal function form |
| GFR | Effectiveness endpoint measures – Renal function | Case report form | Captured from laboratory assessment- Renal function form |
| Transfusions | Safety endpoint measures | Case report form | Captured from transfusions form |
| Healthcare Resource Utilization | Effectiveness endpoint measures | Case report form | Captured from Healthcare Resource Utilization form |
| PROMIS | Effectiveness endpoint measures | Case report form | Captured from PROMIS form |
| Patient Global Impression of Change (PGI-C) | Effectiveness endpoint measures | Case report form | Captured from Patient Global Impression of Change (PGI-C) form |
| Clinical Global Impression of Change (CGI-C) | Effectiveness endpoint measures | Case report form | Captured from Clinical Global Impression of Change (CGI-C) form |
| Pain Scale | Effectiveness endpoint measures | Case report form | Captured from Pain Scale form |
| Sheehan Disability Scale | Effectiveness endpoint measures | Case report form | Captured from Sheehan Disability Scale form |
| Exercise Tolerance | Effectiveness endpoint | Case report form | Captured from Exercise |

| Variable | Role | Data source(s) | Operational definition |
|----------------------------------|--------------------------|------------------|--|
| | measures | | Tolerance form |
| Pregnancy Testing and Fertility | Safety endpoint measures | Case report form | Captured from Pregnancy Testing and Fertility form |
| SCD Complications/Adverse Events | Safety endpoint measures | Case report form | Captured from SCD Complications/Adverse Events Question form |
| Pregnancy | Safety endpoint measures | Case report form | Captured from Pregnancy Notification and Outcome forms |
| Oxbryta Physician Administration | Exposure measures | Case report form | Captured from Oxbryta Physician Administration form |
| Oxbryta Participant Adherence | Exposure measures | Case report form | Captured from Oxbryta Participant Adherence form |

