4. RESEARCH METHODS

4.1. Study design

This registry is an observational study designed to evaluate the effect of Oxbryta® (Voxelotor) in individuals with SCD. This registry is intended to benefit and support interests of participants, clinicians, regulatory bodies, payers, and industry by obtaining longitudinal data on Oxbryta® (Voxelotor). Approximately 500 participants with SCD who are prescribed and treated with Oxbryta® (Voxelotor) will be enrolled. The study will be conducted at approximately 35 sites in the US.

Any participant who is currently taking Oxbryta® (Voxelotor) or has been prescribed and will initiate treatment with Oxbryta® (Voxelotor), is eligible to participate. Eligible participants will receive treatment with Oxbryta® (Voxelotor) as prescribed by their physicians, as part of their usual care. Participants will be treated and evaluated per standard of care (SOC) and at the physician's discretion.

Participants will be introduced to the study by their health care team and will sign the informed consent form (ICF) or assent prior to any data collection for the study.

[figure not shown]
This study will collect data that are recorded in the participants' medical records and other secondary data sources such as Insurance and Pharmacy Claims. Study data will be collected at regular intervals (no more frequent than every 3 months) and entered in case report forms (CRFs) via an electronic data capture (EDC) system by the study staff.

Regardless of how long participants have been on Oxbryta® (Voxelotor) when they enroll in the study, participants will be followed for up to 5 years after their first dose of Oxbryta® (Voxelotor) treatment, or until they withdraw their consent to participate, or are discontinued from the study. Treatment, including interruptions and restarting treatment, will continue at the discretion of the treating physician, and there are no pre-defined treatment requirements. Participants may receive any additional medications prescribed by their treating physician or have any medical interventions that are deemed appropriate by the treating physician or study doctor. The participant or treating physician may discontinue Oxbryta® (Voxelotor) at any time. Participants who discontinue treatment with Oxbryta® (Voxelotor) earlier than 5 years will continue to be followed on study to collect clinical and health-related quality of life (HRQoL) outcomes for up to 5 years after their first dose of Oxbryta® (Voxelotor) treatment.

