4.7. Statistical methodology and analyses

The following general analysis will be followed for this study, unless otherwise specified.

Unless otherwise specified, continuous/quantitative variables will be summarized using descriptive statistics which will include the number of participants with data to be summarized (n), mean, standard deviation (SD), median, first and third quartile (Q1, Q3), minimum, maximum, and the number of missing observations. Minimum and maximum will be reported with the same number of decimal places as collected in raw data, while mean, median, Q1, Q3 will be reported with one extra decimal place, and SD will be reported with two extra decimal places. Descriptive statistics for categorical/qualitative variables will be presented with number of participants and percentage (%) of participants in each category.

Percentages will not include the missing category and will be calculated over the number of participants with available (non-missing) data. A category with a zero count will be presented as “0” and a category with a 100 percentage will be displayed as “100”.

The annualized incidence rate is defined as total numbers of a given event for all participants divided by the total patient-year where the total patient-year is defined as the sum of total duration (years) as defined in the Section 4.7.1 for all participants.

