4.7.1. Index date and follow-up

The index date is defined as the inform consent date. The Post Oxbryta period is from the first dose of Oxbryta to the date of end of treatment or end of study.

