4.7.2. Risk window definitions

Not applicable.

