4.7.3. Analyses for Effectiveness Endpoint Measures

Since this study was not designed as the efficacy study for different indications that contribute significant information about product safety, the analyses in the SAP are considered fit-for-purpose for an abbreviated clinical study report with data scope including 1) full safety data and 2) limited efficacy data to support the benefit-risk evaluation.

Given the reporting nature of the PROMIS items, the reported PRO response was sparse. Therefore, they were excluded from the planned CSR analyses.

The analyses for effectiveness endpoints are based on full analysis set (Section 4.2). The analyses for the abbreviated CSR focus on hematologic and renal function laboratory parameters and SCD-related clinical events.

Participant disposition, non-SCD medical history, concomitant medication, study drug administration (including dosage changes initiated by the participant and by the physician), demographics and baseline characteristics will be summarized descriptively based on full analysis set.

The descriptive statistics will be provided for the following medications:

- long-acting opioids
- Erythropoiesis-stimulating agents
- Other relevant pain meds (e.g. Gabapentin, Lyrica, Cymbalta)
- SCD disease modification agents (hydroxyurea, Adakveo/crizanlizumab, L-Glutamide/levoglutamide).

The study drug administration will be categorized as 1) < 1 month, 2) >=1, <2 months, 3) < 3 months, 4) >=3 months, < 6 months, 5) >=6 months, < 9 months, 6) >=9 months, < 12

months, 7) ≥ 12 months, < 18 months, 8) ≥ 18 months, < 24 months, 9) ≥ 24 months, < 36 months, 10) ≥ 36 months, < 48 months and 11) ≥ 48 months.

The following effectiveness endpoints will be summarized descriptively:

- Change from pre-Oxbryta treatment period in the following hematologic parameters corresponding to treatment with Oxbryta® (Voxelotol):
 - Hb
 - Hemolysis measures, including % reticulocytes, absolute reticulocytes, bilirubin (total, direct, and indirect)
 - ALT and AST

Analysis: Observed and change from pre-Oxbryta treatment period on Hb, Hemolysis measures will be summarized descriptively ([Section 4.7](#)) by visit

If a queried hemolysis value remained greater than its threshold listed in the table below, the value would be deemed erroneous and excluded from the analysis,

Parameter	Threshold
Reticulocyte Count (absolute)	10,000 $10^{9}/L$
Ferritin	100,000 $\mu g/L$

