6. APPENDICES

6.1. Appendix A: List of tables

Table/Listing	Title	Endpoint
Table 15.1.1	Summary of Participant Disposition - Full Analysis Set	Disposition
Table 15.1.2	Demographics and Baseline Characteristics - Full Analysis Set	Baseline
Table 15.1.3	Medical History – Full Analysis Set	Medical history

Table 15.1.4	Study Drug Administration - Safety Analysis Set	Exposure
Table 15.1.5	Study Drug Administration and Dosage Changes Initiated by the Physician - Safety Analysis Set	Exposure
Table 15.2.1	Change in Hematologic Laboratory -Hb Tests by Visit - Full Analysis Set	Effectiveness
Table 15.2.2	Change in Hematologic Laboratory -Hemolysis measures by Visit - Full Analysis Set	Effectiveness
Table 15.2.3	Change in Chemistry Laboratory - Chemistry measures by Visit - Full Analysis Set	Effectiveness
Table 15.2.4	Change in Renal Function Laboratory Tests by Visit - Full Analysis Set	Effectiveness
Table 15.2.5	Summary of SCD Complications-Full Analysis Set	Effectiveness
Table 15.2.5.1	Summary of Transfusions -Full Analysis Set	Effectiveness
Table 15.2.6	Annualized Incidence Rate of SCD Complications - Safety Analysis Set	Effectiveness
Table 15.2.6.1	Annualized Incidence Rate of Transfusions - Safety Analysis Set	Effectiveness
Table 15.2.7	Summary of Patient Global Impression of Change (PGIC) – Full Analysis Set	HRQoL
Table 15.2.8	Summary of Clinical Global Impression of Change (CGIC) – Full Analysis Set	HRQoL
Table 15.3.1	Treatment Emergent Adverse Events by System Organ Class and Preferred Term by Severity - Safety Analysis Set	Safety
Table 15.3.2	Treatment Related Treatment Emergent Adverse Events by System Organ Class and Preferred Term by Severity- Safety Analysis Set	Safety

Table 15.3.3	Treatment Emergent Serious Adverse Events by System Organ Class and Preferred Term by Severity - Safety Analysis Set	Safety
Table 15.3.4	Pregnancy Outcomes and Fertility listings - Safety Analysis Set	Safety
Table 15.3.5	Individual Listings of Deaths- Safety Analysis Set	Safety
Table 15.3.6	Listing of AEs Leading to Discontinuation of the Study - Safety Analysis Set	Safety
Table 15.3.7	Individual Listing of SAEs - Safety Analysis Set	Safety
Table 15.4	Listing of Concomitant Medication - Safety Analysis Set	Concomitant Medication
Table 15.5.1	Annualized Incidence Rate of Acute Pain Crisis – Safety Analysis Set (With Chronic Pain)	Subgroup
Table 15.5.2	Annualized Incidence Rate of Acute Pain Crisis – Safety Analysis Set (Without Chronic Pain)	Subgroup

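### Event rates intended as on-treatment rates are divided by one unbroken interval that has two possible end dates and no rule for pauses

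*SAP*

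**What the plan says.** **Pauses.** Protocol 9.1.1.1 states: "Treatment, including interruptions and restarting treatment, will continue at the discretion of the treating physician, and there are no pre-defined treatment requirements". SAP 4.1 repeats this.

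**Denominator.** For the annualized incidence rate, SAP 4.7 says that "the total patient-year is defined as the sum of total duration (years) as defined in the Section 4.7.1 for all participants". Section 4.7.1 then says: "The Post Oxbryta period is from the first dose of Oxbryta to the date of end of treatment or end of study". Section 4.7.2, on risk windows, reads "Not applicable". No section subtracts time off drug.

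**What the rates are meant to describe.** SAP 4.7.3 presents the rates of SCD complications and transfusions as covering the treatment period. Protocol 9.11.3 sets rates during Oxbryta treatment against those before the first dose, where appropriate.

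**Other end dates.** SAP 4.3 describes Post-Oxbryta as follow-up for up to 5 years from first dose. For safety, SAP 4.7.4 runs to end of study and uses a dose-pausing or discontinuation date only if the end-of-study date is missing. SAP 4.6 replaces a missing or year-only end-of-treatment date with the end-of-study date.

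**Participant-initiated changes.** SAP 4.7.3 promises a descriptive summary of "study drug administration (including dosage changes initiated by the participant and by the physician". In Appendix A the only dosage-change table is 15.1.5, "Study Drug Administration and Dosage Changes Initiated by the Physician - Safety Analysis Set". Protocol 9.4 lists Oxbryta Participant Adherence as an exposure measure ("Captured from Oxbryta Participant Adherence form"). SAP 4.3 keeps the Physician Administration variable and omits the adherence one.

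**The concern.** A rate meant to describe treatment should have time and events on treatment in it. Here off-drug time can enter in two ways: during a pause followed by a restart, and after permanent discontinuation if the end-of-study date closes the interval. Participants who stop remain under follow-up for up to 5 years from first dose, so the second route is built into the design.

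What is at stake is the pre/post comparison of acute pain crisis and VOC rates in SAP 4.7.5, and the rates of the other SCD complications and transfusions. Two analysts could follow the SAP faithfully and produce different patient-years. Neither result would be sure to match the protocol's target.

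The reporting gap is separate. Tolerability is part of the primary objective, and changes that participants make themselves bear on it. The SAP text promises that summary and the table list does not deliver it.

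**Working it through.** The plan gives no rate, exposure total or power figure to reproduce. What can be checked is how the definition behaves.

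**1. Choice of end date.** Take a participant who stops at year 2 and is followed to year 5.
- First dose to end of treatment: 2 patient-years.
- First dose to end of study: 5 patient-years.
- Ratio 5/2 = 2.5; off-drug share 3/5 = 60%, with no pause at all.

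**2. Pauses.** Let f be the share of the counted interval spent off drug. Counted time is then 1/(1 - f) times drug time: 1/0.85 = 1.18 at f = 15% and 1/0.70 = 1.43 at f = 30%. The documents give no value for f; both are assumed.

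**3. Effect on a post/pre rate ratio.** Let R be the true on-drug rate over the pre-drug rate, and q the off-drug rate over the pre-drug rate. Events off drug are counted along with the time, so

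reported ratio = (1 - f) × R + f × q.

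With R = 0.70 (assumed):

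| q (assumed) | f = 15% | f = 30% |
|---|---|---|
| 0.5 | 0.595 + 0.075 = 0.67 | 0.49 + 0.15 = 0.64 |
| 1.0 | 0.595 + 0.15 = 0.745 | 0.49 + 0.30 = 0.79 |
| 1.3 | 0.595 + 0.195 = 0.79 | 0.49 + 0.39 = 0.88 |

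If off-drug rates return to the pre-drug level (q = 1), the reported ratio is about 0.75-0.79. If the drug does not affect the rate (R = q = 1), nothing changes. If off-drug rates are lower than on-drug rates (q = 0.5), the ratio moves the other way. Neither size nor direction is fixed by the documents.

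**4. Exposure table.** SAP 4.7.3 gives duration categories for study drug administration (Table 15.1.4) but not how duration is calculated, and does not link it to 4.7.1. The definition can matter: a 25-month interval with a 3-month pause falls in the 24-to-36-month category if taken gross. Net of the pause it is 22 months, in the 18-to-24-month category. If the pause is counted only after 28 days (about 0.92 month), the net figure is 25 - (3 - 0.92) = 22.9 months, in the same lower category.

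**5. Current text against current text.** SAP 4.7.3 includes participant-initiated changes; Appendix A and SAP 4.3 do not. This conflict needs no arithmetic.

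**The case against.** The strongest reply is that SAP 4.7.1 names a post-Oxbryta period and never calls it drug time. A rate since first dose is a legitimate quantity, and for safety an inclusive window is often preferred. The protocol's comparison is also qualified, and the SAP describes an abbreviated report with limited efficacy data. This stands as far as the label goes, and a reader who inferred that the SAP equates the whole interval with drug time would go too far. It does not remove the mismatch, because SAP 4.7.3 presents the same rates as treatment-period rates.

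Other stronger readings also fail:
- **Exposure is overstated in Table 15.1.4.** Its duration rule is not stated, so this is possible but not shown.
- **The bias must pull the post rate toward the pre rate.** That needs off-drug rates to equal pre-drug rates, which is an assumption.
- **Pause intervals are already in the data.** SAP 4.7.4 implies a pause date, but nothing shows that restart dates are captured or that the adherence form is dated.
- **Pauses that participants start are invisible.** A dosage change need not be a pause, and physician-initiated changes remain tabulated.

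The version history records removal of the participant table as a deliberate change. That explains the table list but leaves the current 4.7.3 text in conflict with it. A missing table does not by itself alter any denominator.

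A fair caution also applies to the remedy: if clinical events trigger pauses, a rate net of pauses is selective.

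**Conclusion.** The point holds in this form: the SAP's annualized rates do not reliably give the on-treatment rates the protocol asks for, because the interval has an unresolved end date and no pause rule. The end-date choice may well matter more than pauses: 5 against 2 patient-years for a stop at year 2 with follow-up to year 5.

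The effect on the rates is not known. The 0.75-0.79 illustration rests on three assumed inputs: a true ratio of 0.70, off-drug rates equal to pre-drug rates, and 15-30% of time off drug. It should not be read as an estimate of bias.

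The duration behind Table 15.1.4 is undefined, which is a gap and not a demonstrated overstatement. The conflict over participant-initiated changes is established from the text alone. Overall this is a cheap improvement worth making; it does not show that the planned analyses are invalid.

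**What to change.** 1. In SAP 4.7.1, define the interval for on-drug rates as first dose to end of treatment. Show first dose to end of study separately, labelled as a since-first-dose rate. Apply the same window to events and time; SAP 4.7.5 gives the post-treatment VOC count a start but no end.
2. Keep these gross rates and add a sensitivity rate that removes recorded, dated pauses, both time and events. A pause would start after the 28-day window that SAP 4.7.4 already uses for treatment-emergent events.
3. Define the duration behind Table 15.1.4, gross and net of recorded pauses.
4. Restore the participant-initiated summary to Appendix A and the adherence variable to SAP 4.3, so that both match SAP 4.7.3.

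The cost is SAP wording, a derived on-drug interval and one restored table. Net exposure figures will be smaller. Pauses without both a start and a restart date stay in net time, and end-of-treatment dates replaced under SAP 4.6 can still carry off-drug time. Because net rates may be selective, they belong beside the gross rates and should not replace them.

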9.3. Study Population

All participants at each participating study site who have been treated with Oxbryta® (Voxelotor) will be considered for inclusion in this study.

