9.3.1. Inclusion Criteria

[figure not shown]
Evidence of a personally signed and dated informed consent document indicating that the patient (or a legally acceptable representative) has been informed of all pertinent aspects of the study.

Participants who meet all the following criteria will be eligible for enrollment in this study:

1. Willing and able to provide written informed consent (aged ≥ 18 years), parental/guardian consent and participant assent (aged ≥ 12 to <18 years) per local regulations, or pediatric participants (aged 4 to <12 years) with parental/guardian consent per Institutional Review Board (IRB) policy and requirements, consistent with ICH guidelines
2. Male or female participants with documented diagnosis of sickle cell disease (all genotypes)
3. Participants who are currently taking Oxbryta® (Voxelotor) or have been prescribed and will initiate treatment with Oxbryta® (Voxelotor) according to the Oxbryta® (Voxelotor) USPI

When participants have been prescribed Oxbryta® (Voxelotor) and deemed eligible to participate in the registry study based on the inclusion/exclusion criteria, they will be enrolled in the study regardless of whether they have started taking Oxbryta® (Voxelotor). After enrollment into the study, it is recommended that the site perform the pre-Oxbryta® (Voxelotor) participant assessments as soon as possible. Once the first dose of Oxbryta® (Voxelotor) treatment has been administered, the participants will be followed for up to 5 years. Patient enrollment process flow is in [Figure 2](#).

Figure 2. Enrollment Process Flow

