3.3 Safety Endpoint Measures

- Rate and severity of serious adverse events (SAEs) and adverse events (AEs) of interest
- Rate of AEs leading to dose modification or discontinuation of Oxbryta® (Voxelotor)
- Pregnancy outcomes and fertility

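### Post-Oxbryta patient-years start at first dose although people already on drug may enrol, so the annualized rates carry unexamined prevalent-user selection and should be split by initiator status

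*SAP*

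**What the plan says.** SAP 4.7 defines an annualized incidence rate as total events over total patient-years, where "the total patient-year is defined as the sum of total duration (years) as defined in the Section 4.7.1 for all participants". SAP 4.7.1 supplies that duration: "The Post Oxbryta period is from the first dose of Oxbryta to the date of end of treatment or end of study". The same section says "The index date is defined as the inform consent date", but consent is not used to start person-time. SAP 4.7.2 gives risk windows as not applicable, and no delayed entry or new-user analysis appears.

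Eligibility is open to existing users. Protocol 9.3.1, criterion 3, admits "Participants who are currently taking Oxbryta® (Voxelotor) or have been prescribed and will initiate treatment". Protocol 9.1.1.1 and SAP 4.1 apply the five-year follow-up from first dose "Regardless of how long participants have been on Oxbryta® (Voxelotor) when they enroll in the study". SAP 4.2 and 4.4 bring in exposure and data from the RETRO study.

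Collection also reaches back before consent. Protocol 9.7 starts data entry at the first commercial dose, using records only. Protocol 10.3.6.1.2 records all post-treatment complications since the last timepoint. SAP 4.7.5 counts post-Oxbryta VOCs from treatment start.

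Annualized rates are listed in SAP Appendix A only for SCD complications (Table 15.2.6), transfusions (15.2.6.1) and acute pain crisis (15.5.1 to 15.5.5). SAP 3.3 calls SAEs and AEs leading to dose modification or drug discontinuation rate endpoints. SAP 4.7.4 and Appendix A give safety events frequency tables or listings, with no patient-year denominator.

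**The concern.** Someone who started the drug and died before being approached cannot enrol. Under criterion 3, neither can someone who had stopped for good. Their early events and early patient-years are absent, while the early patient-years of those who reached consent are counted. Approval was in November 2019 (Protocol 7.1.2) and data collection started on 02 February 2022 (Protocol 6), so about 2.2 years of earlier commercial use was possible even for the first enrollee.

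If early leavers had more pain crises or responded poorly, the post-Oxbryta rate describes a better-than-average group of initiators. Records-based capture adds a second risk: an event before consent that was treated elsewhere may be missed while the time is counted. The pre/post pain-crisis rates in SAP 4.7.5 are the plan's main effectiveness contrast, and the planned tables give no way to see either effect.

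**Working it through.** The documents state no rate, event count, person-time or power figure (SAP 4.5: no formal sample size calculation), so there is no plan figure to reproduce. The checks below use assumed inputs.

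Notation: f = share of participants already on drug at consent; L = their mean time from first dose to consent; F = mean follow-up after consent; c = fraction of pre-consent events captured. None is in the documents. Assumed ranges: f 25% to 75%, L 0.5 to 2 years, F 1 to 2 years.

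**1. Recurrent events, constant rate, stopping unrelated to the event.** Rate as planned ÷ true rate = (F + c·f·L) / (F + f·L).

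- c = 1: ratio 1.00 for every f, L and F. Time and events start together.
- c = 0.5, f = 0.5, L = 1, F = 2: (2 + 0.25) / 2.5 = 0.90.
- c = 0.5, f = 0.75, L = 2, F = 1 (extreme): (1 + 0.75) / 2.5 = 0.70.

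**2. Recurrent events, informative stopping, full capture.** Simulation, 400,000 participants per scenario. VOC rate averages 2/year. Stopping hazard is 0.4/year times a personal factor to the power b; existing users enrol only if still on drug. Lead time is uniform over 0 to 2.2 years, with up to 3 years after consent and a cap of 5 years from first dose; f is 25%, 50% or 75%. The factor is either underlying VOC frailty (gamma, mean 1, variance 0.5) or individual response on drug (lognormal, mean 1, log-SD 0.4; high = poor). The target is the on-treatment rate in all initiators.

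| Stopping depends on | b | First-dose clock ÷ target | Consent clock ÷ target |
|---|---|---|---|
| Neither (b = 0) | 0 | 1.000 | 0.998 to 1.001 |
| Frailty | 0.5 to 2 | 0.943 to 0.992 | 0.928 to 0.991 |
| Response | 0.5 to 2 | 0.975 to 0.997 | 0.965 to 0.995 |
| Frailty | -1 | 1.013 to 1.038 | 1.011 to 1.051 |
| Response | -1 | 1.005 to 1.016 | 1.004 to 1.025 |

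So the rate is 0.94 to 1.00 of target when high-rate or poor-response people stop earlier, and slightly above target in the opposite case. Moving the clock to consent does not recover the target.

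**3. Pre/post contrast in the same runs** (b = 1, f = 50%). Post ÷ pre among those enrolled against all initiators: 0.822 against 0.793 when stopping follows frailty, so selection makes the drug look slightly worse; 0.909 against 0.919 when it follows response, so slightly better. The direction depends on why people stop.

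**4. Terminal outcomes (death, drug discontinuation).** These cannot occur before consent in anyone enrolled under criterion 3. With constant hazard, first-dose clock ÷ delayed-entry rate = F / (F + f·L).

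- f = 0.25, L = 0.5, F = 2: 2 / 2.125 = 0.94.
- f = 0.75, L = 2, F = 1: 1 / 2.5 = 0.40.

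Here the time is immortal in the strict sense, but Appendix A contains no patient-year rate for these outcomes.

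**The case against.** A reader might infer that first dose to consent is immortal time and that the planned rates are therefore biased low by a large amount. For example, take an AE-discontinuation hazard of 0.20/year, follow-up to 3 years, and consent uniform over 0 to 1 or 0 to 2 years. The first-dose clock then returns 0.161 or 0.128, which is 20% or 36% low. With 0.4/year for six months and 0.1/year after, the true rate is 0.160 and the clock returns 0.096 or 0.073, which is 40% to 54% low. The documents do not support carrying these figures over. They concern a terminal outcome with no planned person-time rate, and they make every participant an existing user. For VOC, other non-fatal complications and transfusions, pre-consent events are counted.

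Other points against also stand:

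- A consent clock would discard validly collected early events and leave a gap after the 12-month pre-period. In the front-loaded example it still gives 0.118 or 0.112 against 0.160, or 26% to 30% low.
- The pre-period is equally conditional on reaching consent, so stable differences between people affect both sides of the contrast.
- That nobody could have stopped before consent is too absolute. Interruptions and restarts are allowed, and Protocol 9.3 is looser than criterion 3: "All participants at each participating study site who have been treated with Oxbryta® (Voxelotor) will be considered for inclusion in this study".
- The net direction is open. SAP 4.7.5 sets no end to post-Oxbryta VOCs, while 4.7.1 may end person-time at end of treatment. If later events were counted over on-treatment time, the same simulation gives 1.46 to 2.01 times the target.
- The outputs are descriptive, and Protocol 9.13 discloses susceptibility to bias in comparing outcomes.

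What survives is that a general disclosure does not let a reader see how far the rates depend on existing users.

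**Conclusion.** The selection is real and is built into SAP 4.7 and 4.7.1 together with criterion 3. It is prevalent-user selection, not immortal time, for every annualized rate now planned. Those rates are likely low, but only if people with more events or poorer response left earlier, or if pre-consent events are under-recorded. Under the assumptions shown, the first gives 0.94 to 1.00 of the all-initiator rate and the second about 0.90 at 50% capture (0.70 at the extreme). With neither, the ratio is 1.00. The share of existing users, their lead time, the capture fraction and the reasons for stopping are not in the documents, so the actual size is unknown.

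Strict immortal-time bias would arise only if a patient-year rate were produced for death or for AEs leading to drug discontinuation. SAP 3.3 uses the word rate for the latter, so this should be guarded against. The plan is not wrong as written on this point; the change is a cheap improvement.

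**What to change.** In Tables 15.2.6, 15.2.6.1 and 15.5.1 to 15.5.5:

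- Keep the first-dose clock for the main rate.
- Add separate columns for participants whose first dose was before consent and those whose first dose was on or after consent, with the number of participants and patient-years in each.
- Add a sensitivity analysis that starts both patient-years and events at the later of first dose and consent. State that it does not remove prevalent-user selection.

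In SAP 4.7, add that any person-time rate for death or for AEs leading to drug discontinuation will use delayed entry at the later of first dose and consent. Give the post-Oxbryta numerator and denominator the same stated end, and reconcile the population wording in Protocol 9.3 and SAP 4.2 with criterion 3.

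The cost is SAP wording and programming; consent and first-dose dates are already needed for the plan's own index date and periods. The downside is extra columns and less precise rates within each stratum.
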